(1) Drug treatment group: Patients clinically diagnosed with early pregnancy missed abortion who chose drug treatment were divided into groups according to their own wishes. Patients in the routine group were given mifepristone 50mg twice a day for two consecutive days on the first day, and misoprostol 600µg vaginally or 400µg sublingually on the third day. Patients in the experimental group were given estradiol valerate tablets 2mg twice a day for three days in addition to the treatment given to group A.

① The gestational sac is completely expelled, and the bleeding is less than menstrual flow. There are no contraindications to estrogen use. Patients can choose to take different doses of estrogen after medical abortion based on their own wishes. Group A (the standard group) does not require estrogen supplementation after medical abortion. Group B (the standard group) uses the standard dose of estrogen after medical abortion: 1 day after medical abortion (as above), oral estradiol valerate 1mg twice daily for 21 days, followed by dydrogesterone 10mg for the last 7 days. B i d , starting from day 5 of the next menstrual period, for a total of 2 cycles. Group C was the conventional group, using high-dose estrogen after medical abortion: 1 day after medical abortion (as above), estradiol valerate 2mg was administered orally . B i , 21 days, with dydrogesterone 10mg added for the last 7 days. B i d , starting from day 5 of the next menstrual period, for a total of 2 cycles. Group D (experimental group) did not receive estrogen supplementation after medical abortion. Group E (experimental group) received conventional doses of estrogen after medical abortion: 1 day after medical abortion (as above), estradiol valerate 1mg orally B i d, 21 days, followed by dydrogesterone 10mg for the last 7 days. B i d , starting from day 5 of the next menstrual period, for a total of 2 cycles. Group F was the experimental group, which received high-dose estrogen after medical abortion: 1 day after medical abortion (as above), estradiol valerate 2mg was administered orally . B i , 21 days, with dydrogesterone 10mg added for the last 7 days. B i d , starting from day 5 of the next menstrual period, for a total of 2 cycles. ② If the

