did not take estradiol valerate tablets before the curettage and underwent hysteroscopic curettage directly under ultrasound guidance . No estrogen supplementation was given after the procedure. Group H did not take estradiol valerate tablets before the curettage and underwent hysteroscopic curettage directly under ultrasound guidance . Starting from the first day after the procedure , estradiol valerate was administered orally , 1 mg twice daily for 21 days, and dydrogesterone 10 mg was added for the last 7 days. Two cycles of estradiol valerate were administered starting on day 5 of the next menstrual period . Group I did not take estradiol valerate tablets before the curettage and underwent hysteroscopic curettage directly under ultrasound guidance . From the first day after the procedure , estradiol valerate was administered orally , 2 mg twice daily for 21 days, followed by an additional 10 mg of dydrogesterone for the next 7 days. Two cycles of estradiol valerate were administered, starting on day 5 of the next menstrual period. Group J received 2 mg estradiol valerate orally three days prior to the procedure, followed by hysteroscopic curettage under ultrasound guidance on day 4. No estrogen supplementation was administered post-procedure. Group K received 2 mg estradiol valerate orally three days prior to the procedure , followed by hysteroscopic curettage under ultrasound guidance on day 4. Post-procedure , estradiol valerate was administered orally at 1 mg twice daily for 21 days, with an additional 10 mg dydrogesterone for the following 7 days. B i d , starting from day 5 of the next menstrual period, for a total of 2 cycles. Group L took estradiol valerate tablets orally for 3 consecutive days before the curettage , at a dose of 2mg B i d . On day 4, the curettage was performed under ultrasound guidance via hysteroscopy . From the first day after the procedure , estradiol valerate was taken orally , 2mg B i d, for 21 days, followed by dydrogesterone 10mg for the last 7 days. B i d , starting from the 5th day of the next menstrual period, for a total of 2 cycles. All surgically treated patients received an intrauterine injection of sodium hyaluronate gel after curettage to prevent intrauterine adhesions .

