For all patients with missed abortions, treatment to promote uterine contraction after the expulsion of the pregnancy tissue includes: routine intravenous administration of uterotonic agents (oxytocin is commonly used , and ergonovine may be used if

necessary) ; and oral administration of uterotonic drugs (such as Wujia Shenghua capsules) for 2 weeks. Infection prevention: If signs of infection or high-risk factors for infection are present, antibiotics may be used as appropriate, and the type, route of administration, dosage, frequency, and duration of administration of antibiotics must be accurately recorded. Pathological examination: The pregnancy tissue expelled during the procedure is routinely sent for pathological examination; chromosomal analysis of the abortion tissue is performed based on the patient's preference.

End of treatment sign:

(1) A follow-up ultrasound showed no retained products of conception, and serum HCG levels returned to normal; (2) Patients with retained products of conception underwent clinical observation or curettage.

5. Key Evaluation Indicators

(1) Evaluation indicators before treatment: patient's age, time of consultation, gestational week of termination of pregnancy, symptoms, ultrasound findings of uterine size, gestational sac size and location, serum HCG level, parity , number of previous intrauterine procedures, and whether there are other intrauterine diseases before pregnancy (such as intrauterine adhesions, uterine septum , submucosal fibroids).

(2) Routine examination data after admission: routine vaginal discharge test, HPV/TCT, routine blood tests, liver and kidney function tests, electrolyte test , coagulation function test, thyroid function test, blood β -HCG test, anti-Müllerian hormone test, pre-transfusion examination, electrocardiogram, chest X-ray, uterine and bilateral adnexa 2-D/3-D color Doppler ultrasound and other related examinations.

(3) During drug treatment: the type and dosage of drugs taken, the time of expulsion of the gestational sac, the amount of vaginal bleeding, adverse drug reactions, etc.

(4) Surgical data: Date of surgery; depth of uterus; location and size of the gestational tract; operation time (from the start of the distension procedure to the withdrawal of the endoscope); amount of intraoperative blood loss; whether there is any retained gestational tract after surgery; clarity of the intraoperative field of vision;

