volume of distension fluid in and out; whether there is a decrease in blood oxygen saturation; whether complications such as uterine perforation, acute left heart failure, or gas embolism occur. Postoperative follow-up data : serum β -HCG, complete blood count, CRP, procalcitonin (not necessary), ultrasound to check for retained gestational tract, and if so, record the maximum diameter of the retained tract.

(5) Outpatient follow-up data 3 months after treatment : duration of vaginal bleeding after miscarriage, amount of bleeding, time of menstruation resumption , changes in menstrual flow , whether ultrasound indicates intrauterine adhesions, condition of endometrium, whether intrauterine adhesion surgery was performed, and intrauterine adhesion score.

(6) Pregnancy outcomes: Pregnancy rate after 1 year of trying to conceive (followed up every 6 months) ; spontaneous abortion rate, premature birth rate, full-term birth rate, stillbirth rate in subsequent pregnancies.

Follow-up data is used only for clinical efficacy evaluation.

6. Safety considerations

The data in this study are derived from clinical data and are absolutely safe. The use of estrogen for missed abortion is in accordance with routine clinical treatment, with the standard dose being 2 mg. 4 mg of estrogen is an off-standard dose, but numerous domestic and international studies have shown that high-dose estrogen for women of childbearing age without contraindications to estrogen use can effectively improve patients' clinical symptoms and has a high safety profile.

7. Statistical Analysis

using SPSS 26.0 software. Normally distributed measurement data were expressed as ($\bar{x} \pm s$), and t-tests were used for comparisons between two groups, while ANOVA was used for comparisons among multiple groups. Non- normally distributed measurement data were expressed as the median, and a nonparametric rank-sum test was used . Categorical data were analyzed using the χ^2 test or Fisher 's test. $P < 0.05$ was considered statistically significant.

8. Data integrity and quality assurance

Researchers should ensure that data is authentic, accurate, complete, and traceable, and should ensure the integrity of basic clinical research documents during retention, avoiding intentional or unintentional alteration or loss.

9. Ethical Statement

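### Time to menstrual resumption cannot be compared between post-treatment hormone users and non-users in the prospective part, because the tablet schedule times the users' first bleed

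*Protocol*

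**What the plan says.** **Endpoints.** Protocol Section 5, item (5), is headed "Outpatient follow-up data 3 months after treatment" and includes "time of menstruation resumption , changes in menstrual flow , whether ultrasound indicates intrauterine adhesions, condition of endometrium". Section 5 closes by reserving follow-up data for the evaluation of clinical efficacy.

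**Groups without post-treatment hormones.** In Section 4 (Research Process, Treatment methods, prospective study), "Group A (the standard group) does not require estrogen supplementation after medical abortion", and D is likewise untreated afterwards. For surgical group G, "No estrogen supplementation was given after the procedure", and J is the same.

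**Groups with post-treatment hormones.** Group B takes "oral estradiol valerate 1mg twice daily for 21 days, followed by dydrogesterone 10mg for the last 7 days", starting one day after the medical abortion. C, E and F follow the same pattern. Group H takes "1 mg twice daily for 21 days, and dydrogesterone 10 mg was added for the last 7 days" from the first day after the procedure, and L follows the same pattern. For I and K the text puts dydrogesterone in the seven days after the 21.

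**Repeat courses.** All eight groups restart on day 5 of the next period. B, C, E, F, K and L are limited to two cycles in total. For H the text reads "Two cycles of estradiol valerate were administered starting on day 5 of the next menstrual period", with near-identical wording for I. That can be read as two courses beyond the first.

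**Comparison.** Section 4 (Grouping) divides women by no, standard-dose and high-dose estrogen and then analyses the data. Section 7 sends multi-group comparisons to ANOVA or a rank-sum test.

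**The concern.** Section 1 argues that estrogen may promote endometrial repair, and return of menses is an obvious outcome to read as evidence of it. In the four untreated groups the first bleed is a spontaneous return. In the eight treated groups it is the bleed that follows the end of a hormone course. The protocol treats it as an ordinary period and starts the next course from its fifth day. One variable name therefore covers two different events, and the split between them is exactly the estrogen contrast that the study wants to make.

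At stake is a claim that estrogen speeds (or slows) menstrual recovery when only the tablet calendar differs. The estrogen-versus-none contrast is wholly of this kind. So are 4 × 8 = 32 of the 12 × 11 / 2 = 66 pairwise group comparisons.

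**Working it through.** The plan gives no figure to reproduce for this endpoint. The check is a calendar built from the regimen in Section 4.

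**Inputs**
- Course length L: 21 days, or 21 + 7 = 28 if dydrogesterone follows the 21 days (the wording for I and K).
- First tablet: about day 1 after the abortion.
- Next course: starts on day 5 of the following bleed, which is bleed date + 4.
- Lag w from last tablet to bleed: not in the protocol; assumed to be 2 to 7 days.
- Visit: about day 90, if the 3 months run from the abortion.

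**Formulas**
- End of course 1 = L.
- Bleed k = end of course k + w.
- End of course k+1 = bleed k + 4 + L − 1.

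**Example (L = 21, w = 2).** Course 1 ends on day 21 and the bleed is on day 23. Course 2 ends on 23 + 4 + 20 = day 47 and the bleed is on day 49. A third course would end on 49 + 24 = day 73.

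| | L = 21, w = 2 to 7 | L = 28, w = 2 to 7 |
|---|---|---|
| First bleed | day 23-28 | day 30-35 |
| Last tablet, two courses | day 47-52 | day 61-66 |
| Days from last tablet to day 90 | 43-38 | 29-24 |
| Bleed after course 2 | day 49-59 | day 63-73 |
| Last tablet, three courses | day 73-83 | day 94-104 |
| Days from last tablet to day 90 | 17-7 | −4 to −14 |

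**Resumption.** On every reading the first bleed is set by the course end.

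**Flow.** With two 21-day courses, the bleed after the second course is on day 49-59. That leaves 90 − 59 = 31 to 90 − 49 = 41 days before day 90, so one spontaneous bleed can occur. With two 28-day courses only 17 to 27 days remain.

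**Endometrium.** The ultrasound falls from about 6 weeks after the last tablet (two 21-day courses) to during a course (three 28-day courses). No cycle day is fixed.

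**Size of the artefact.** This needs the natural return date, which the protocol does not give. Assume a mean of 28 to 42 days.
- 21-day course: users bleed between 28 − 28 = 0 and 42 − 23 = 19 days earlier than non-users.
- 28-day course: the gap runs from 28 − 35 = −7 (users later) to 42 − 30 = 12 days.

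**Illustration of the risk.** Assume natural return at day 35, a scheduled bleed at day 28, SD 10 in both arms, and 180 / 12 = 15 women per group, giving 60 without and 120 with hormones.
- Standard error = 10 × √(1/60 + 1/120) = 1.58.
- 7 / 1.58 = 4.43, and 4.43 − 1.96 = 2.47, so the chance of a significant result at two-sided 0.05 is about 99%.
- For one group against another (15 vs 15) the standard error is 10 × √(2/15) = 3.65 and the chance is about 48%.
- If natural return is also at day 28, the gap is 0 and there is no spurious effect in the means.

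**Standard versus high dose.** If the I and K wording is taken literally, H versus I and K versus L each differ by 28 − 21 = 7 days in first bleed. In the first pair the high-dose group is later; in the second, the standard-dose group is.

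**The case against.** The strongest reply is that Section 5 only lists data to collect. It names no primary endpoint and no specific menstrual contrast, and the definition of resumption may stand in an analysis plan that is not shown. This stands in part, since an analysis plan could define the variable sensibly. But the protocol fixes the estrogen grouping, the hormone calendar and the use of these data for efficacy. Section 5 lists the drugs taken during drug treatment, but not the dates of the later hormone courses or the cycle day at the ultrasound. An analysis plan cannot recover dates that were not recorded.

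The other objections limit the scope, and they are right:
- **Endometrium.** A reader might infer that the endometrial reading also records a withdrawal bleed. It does not; it is an imaging finding. The sound criticism is its unfixed timing relative to hormones.
- **All bleeds.** A reader might infer that every bleed before the visit is hormone-driven. With two 21-day courses the last one may be spontaneous.
- **Still on hormones at the visit.** A reader might infer this for both I and K. K is limited to two cycles in total, which ends on day 61-66 when the first course is counted. Only I's wording, read as two further 28-day courses, passes day 90.
- **Guaranteed false benefit.** The calculation does not support this. The gap can be zero or reversed.
- **Clock.** Section 4 gives as an end-of-treatment sign that "A follow-up ultrasound showed no retained products of conception, and serum HCG levels returned to normal". If the 3 months start there, the visit is later than day 90 from abortion and the hormone-free interval is longer. The first bleed is still set by the course.
- **Partial expulsion.** These women take estradiol for an open waiting period before an artificial cycle, so the calendar above does not describe them.

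**Conclusion.** The point holds for time to menstrual resumption in the prospective none-versus-estrogen contrast. In eight of the twelve groups the course end fixes the first bleed, at day 23-28 or day 30-35 depending on the wording, given an assumed lag of 2 to 7 days. A difference from the four untreated groups would not measure endometrial recovery. With natural return assumed at 28 to 42 days, the artefact runs from users bleeding 7 days later to 19 days earlier. Its size and direction are therefore unknown, but the contrast is invalid whichever way it falls.

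Menstrual flow is affected in part, to an extent that depends on the number and length of courses. The endometrial ultrasound lacks a fixed relation to hormone use. The adhesion items, and the retrospective comparison of drug with surgical treatment, are not affected on the text.

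**What to change.** 1. State that no none-versus-estrogen efficacy claim will be made from the date of first bleed. Redefining the endpoint as first spontaneous menses does not rescue it. Timing from the last tablet in some groups and from evacuation in others gives different clocks.
2. Record the date of the last hormone tablet, whether each bleed occurred on or off hormones, and the hormone status and cycle day at the 3-month ultrasound.
3. Compare change in flow in the first hormone-free cycle.
4. Rest the estrogen comparison on endpoints that the regimen does not set: intrauterine adhesions and subsequent pregnancy.
5. Limit any comparison of resumption time to standard versus high dose, and only once the protocol is reconciled on three matters: whether dydrogesterone falls within or after the 21 days (I and K against the other groups), whether the two cycles include the first course, and when the 3 months after treatment begin.

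None of this requires a change of treatment. The cost is endpoint wording and a few case-report fields. Women still on hormones, or without a hormone-free cycle by the 3-month visit, would need a short added question or call. The 6-monthly contact in Section 5, item (6), is listed only for pregnancy outcomes, so it cannot be assumed to cover this.

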A real-world study comparing the efficacy of different treatment options for early missed miscarriage.

Funding source: None

Research Institution: Xiangya Third Hospital, Central South University

Research Leader: [name]

Version number: 1.0

Version date: 2023.11.21

A handwritten signature in black ink, appearing to be '[name]' ([name]), the research leader.

Table of contents

Research Proposal Summary	3
Research Text	6
1. Research Background	6
2. Research Objectives	7
3. Research Design	8
4. Research Content	10
5. Key Evaluation Indicators	16
6. Safety considerations	17
7. Statistical Analysis	17
8. Data integrity and quality assurance	18
9. Ethical Statement	18
10. References	18

Research Proposal Summary

Experiment title:

A real-world study comparing the efficacy of different treatment options for early missed miscarriage.

Research objective:

Currently, there is no unified standard for the treatment of missed abortion in clinical practice. This study aims to collect clinical data on this type of disease to compare the differences in efficacy of different treatments. Based on this, it will also explore the synergistic effect of combining different doses of estrogen with medical induction of labor, conduct statistical analysis on the efficacy, and evaluate whether the treatment plan achieves the desired therapeutic effect while reducing the occurrence of complications, thus providing a valid basis for the subsequent clinical treatment of missed abortion.

Experimental Design:

This study is divided into two parts. The first part is a retrospective analysis, which explores the differences in clinical efficacy and reproductive outcomes between surgical and medical treatment for missed abortion. The second part is a prospective study, which explores the impact of different doses of estrogen combined with surgical or medical abortion on the efficacy of early pregnancy missed abortion, and seeks the optimal clinical treatment method for missed abortion .

Experimental procedure:

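### No follow-up item names reactions to estradiol or dydrogesterone, although most scheduled estrogen is taken in that period, and follow-up data are reserved for efficacy

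*Protocol*

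**What the plan says.** The objective, in the summary and again in section 2, is to "evaluate whether the treatment plan achieves the desired therapeutic effect while reducing the occurrence of complications".

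Section 5 sets out what is recorded. Item (3), on the period of drug treatment, includes "the amount of vaginal bleeding, adverse drug reactions, etc". Item (4) covers the operation and the postoperative checks. Item (5) is the 3-month outpatient visit and item (6) is later pregnancy. The section closes with "Follow-up data is used only for clinical efficacy evaluation".

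Section 6 opens with "The data in this study are derived from clinical data and are absolutely safe". On estrogen it continues "with the standard dose being 2 mg", and then "4 mg of estrogen is an off-standard dose". It describes no recording or review of harms.

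The treatment methods place the estrogen courses mainly after the abortion or procedure. Group F is the experimental drug group "which received high-dose estrogen after medical abortion: 1 day after medical abortion". In surgical group L, "estradiol valerate was taken orally , 2mg B i d, for 21 days", with further treatment from the next menstrual period.

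**The concern.** A study whose aim includes fewer complications, and which compares a standard with an off-standard estrogen dose, needs a record of reactions to that estrogen while it is being taken. As written, the item that names adverse drug reactions belongs to the abortion phase, the follow-up items do not name them, and the closing sentence of section 5 gives follow-up data one use, efficacy.

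If staff build the case record form from section 5, a thromboembolic event or an early stop in week three of estradiol has no field. A report could then state that no estrogen-related harm was seen when nothing on the form asked about it. The plan does recognise the risk: thromboembolic disease and contraindications to estrogen are exclusion criteria.

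**Working it through.** **1. Where harms are listed**

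| Place in the Protocol | Harms named | Drug reactions named? |
|---|---|---|
| Summary, experimental procedure: treatment-phase list | blood loss, vaginal bleeding, adverse drug reactions | Yes, not limited to drug patients |
| Summary: follow-up list | bleeding, menstrual change, later pregnancy | No |
| Section 5 item (3) | vaginal bleeding, adverse drug reactions | Yes, beside the time of sac expulsion |
| Section 5 item (4) | perforation, acute left heart failure, gas embolism, desaturation, blood loss, retained tissue; postoperative blood count, CRP, procalcitonin | No |
| Section 5 item (5) | bleeding, menstrual change, endometrium, adhesions, adhesion surgery and score | No |
| Section 5 item (6) | miscarriage, preterm birth, stillbirth | No |

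The summary and section 5 therefore differ on surgical patients during treatment, and agree that the follow-up lists contain no drug-reaction item.

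**2. Where the estrogen exposure falls**

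Inputs come from the treatment methods: 3 days of estradiol before treatment in the pre-treated groups, and 21-day courses afterwards for a stated total of 2 cycles. The total can be read as two courses (2 × 21 = 42 days) or as the first course plus two more (3 × 21 = 63 days). The regimens for J and K are worded less fully than that for L; I read all three as 3 days.

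Share of estradiol days after the procedure = days after ÷ (days before + days after).

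| Groups | Before | After | Share after |
|---|---|---|---|
| A, G | none | none | – |
| D, J | 3 days | none | 0% |
| B, H | none | 1 mg × 2 = 2 mg/day | 100% |
| C, I | none | 2 mg × 2 = 4 mg/day | 100% |
| E, K | 3 days | 2 mg/day | 42/45 = 93.3% to 63/66 = 95.5% |
| F, L | 3 days | 4 mg/day | 93.3% to 95.5% |

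The daily totals of 2 mg and 4 mg match the two doses described in section 6. Eight of twelve groups take most or all of their scheduled estrogen after the procedure, and four of them at 4 mg a day. Dydrogesterone is given only in these post-procedure courses.

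**3. What complete recording could show**

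The plan states 180 prospective cases and no group sizes; women choose their group. Equal groups are an assumption: 180/12 = 15 per group, so 4 × 15 = 60 women on post-procedure 4 mg a day, 30 of them surgical. With zero events in n women, the one-sided 95% upper limit is 1 − 0.05^(1/n).

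| n | Upper limit with zero events | Chance of at least one event if the true rate is 1% |
|---|---|---|
| 30 | 9.5% | 26% |
| 60 | 4.9% | 45% |
| 90 | 3.3% | 60% |

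The row for 90 shows the effect of more women choosing the higher dose. These limits describe the sample size. They would be the same after the lists are corrected and do not measure the recording gap.

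**The case against.** Four points can fairly be made for the plan.

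- **Surgical patients are not ignored.** A reader of section 5 alone might infer that drug harms go unrecorded throughout the surgical groups. The summary does not support that, since its single treatment-phase list covers surgical and drug patients alike. This stands. But that list precedes the summary's follow-up list, which names no drug reactions, so the post-procedure courses remain uncovered.
- **Many complications are collected.** The background names perforation, infection, adhesions, incomplete abortion and menstrual disorder, and most of these have items or markers in section 5; antibiotic use is recorded as well. It would be wrong to infer that the complications part of the objective cannot be answered. What lacks an item is harm from the estrogen itself.
- **The safety sentence is about data.** One might read section 6 as declaring the off-standard dose absolutely safe. Literally, its subject is the data of a study that adds no intervention or test, and the doses come in later sentences, with the favourable safety claim limited to women without contraindications. So there is no strict contradiction. It is still the opening safety statement, and the origin of the data says nothing about the dose.
- **The wording is loose.** The efficacy-only sentence may mean only that data serve no outside purpose, and adhesions and pregnancy loss sit under it although they are harms. Item (3) is open-ended and might be stretched to the estrogen course. Both readings are possible, but a plan should not depend on them, and sac expulsion in item (3) points to the abortion phase.

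**Conclusion.** The point holds in a limited form. During follow-up, when 93% to 100% of scheduled estradiol days fall in eight of the twelve groups, no listed item asks about reactions to estradiol or dydrogesterone, and the stated use of follow-up data conflicts with the objective on complications. The percentages assume that the scheduled regimens are followed and depend on how the two cycles are counted; either reading leads to the same conclusion.

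The figure of about 5% for 60 women rests on equal groups and is background only. It shows how cautiously an absence of events should be reported. This is a low-cost improvement to the recording plan. It does not invalidate the efficacy comparison.

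**What to change.** - Reconcile the summary's two lists with section 5 items (3) to (5), so that adverse drug reactions are recorded in all prospective groups A to L, including pre-treated group J, through the whole estrogen course.
- Add to item (5): adverse reactions to estradiol or dydrogesterone, including thromboembolic events; early stopping and its reason; infection; unplanned readmission.
- Reword the closing sentence of section 5 so that follow-up data serve both efficacy and safety evaluation.
- Replace the opening sentence of section 6 with a statement that safety will be evaluated from these data.
- Report these harms by estrogen level with confidence limits, including the upper limit where no event is seen. The detail can sit in the SAP.

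The cost is a few more questions at the 3-month visit already planned and a less favourable safety statement. No dose, treatment rule or additional test is involved.
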